## 5.0 Procedures Involved

### 5.1 Study Design:

This is a pilot, pragmatic, randomized trial with 6-month placebo-controlled period followed by a 6-month open label extension. Thirty pubertal or post-pubertal adolescents will be randomized into one of two arms:

- PHN/TPM
- Placebo

MEDICAL PROTOCOL PEDS-2021-29785

PROTOCOL TITLE: Phentermine/Topiramate in Adolescents with Type 2 Diabetes and Obesity

VERSION DATE: 10Dec2024

Participants will engage in typical T2D clinical care and lifestyle management, with the addition of PHN/TPM or placebo therapy for 6 months followed by a 6-month open label extension during which all participants will be given PHN/TPM in an unblinded fashion.

The schedule of events (below) shows the data that will be collected at each study visit.

MEDICAL PROTOCOL PEDS-2021-29785

PROTOCOL TITLE: Phentermine/Topiramate in Adolescents with Type 2 Diabetes and Obesity

VERSION DATE: 10Dec2024

Schedule of Events

Week	Screening	Baseline	Placebo-Controlled												
	-4%	0%	4	8	12%	16	20	24%	28	32	36%	40	44	48	52%
Informed consent/assent	X														
Demographics	X														
Medical and medication history	X														
Review of inclusion/exclusion criteria	X														
Randomization		X													
Urine pregnancy test d	X	X	X	X	X	X	X	X	X	X	X	X	X	X	X
Physical Exam	X	X			X			X			X				X
Tanner staging	X				X			X			X				X
Anthropometrics a	X	X	X	X	X	X	X	X	X	X	X	X	X	X	X
Vital signs (Blood pressure and heart rate)	X	X			X			X			X				X
EKG		X													
Contraceptive counseling	X	X	X	X	X	X	X	X	X	X	X	X	X	X	X
Adverse events			X	X	X	X	X	X	X	X	X	X	X	X	X
Hemoglobin A1c		X			X			X			X				X
Eating Disorder Examination Questionnaire (EDE-Q)		X			X			X			X				X
Peds-QOL (general and diabetes modules)		X						X							X
Patient Health Questionnaire (PHQ-9)	X				X			X			X				X
Columbia-Suicide Severity Rating Scale (C-SSRS)	X				X			X			X				X
Total daily insulin dose assessment		X			X			X			X				X
Oral Glucose Tolerance Test (OGTT)		X						X							X
ALT, AST, INR, TSH, bilirubin, albumin, basic metabolic panel	X							X							X
Lipid profile, vitamin D 1,25 b		X													
Plasma glucose level b		X						X							X
c-peptide level b		X						X							X
Insulin level b		X						X							X
iDXA (visceral and total body fat and bone mineral density)		X						X							X
Review of CGM data c			X	X	X	X	X	X	X	X	X	X	X	X	X
Insulin titration per CGM			X	X	X	X	X	X	X	X	X	X	X	X	X
Dispense new CGM sensor			X	X	X	X	X	X	X	X	X	X	X	X	
Dispense study medication		X	X	X	X	X	X	X	X	X	X	X	X	X	
Review of medication adherence					X			X			X				X
Review of co-administered drugs	X	X			X			X			X				X
Lifestyle and behavior counseling		X			X			X			X				X

Highlighted "X" will be done in the Clinical Research Unit. Non-highlighted X will be done in the Delaware Clinical Research Center

a Including height and weight at Weeks 0, 12, 24, 36 and 52. Weight only will be done at Weeks 4, 8, 16, 20, 28, 32, 40, 44, 48. Weight done remotely via Bluetooth monthly if there are no in-person visit scheduled for weeks 28, 32, 40, 44, and 48.

b Blood will be drawn during the OGTT at baseline, 30-, 60-, 90- and 120-minutes following glucose ingestion

c Continuous glucose monitoring with CGM data will be reviewed with participant via telephone after upload by PI or [name], Clinical Diabetes Educator.

d Urine pregnancy tests will be done on all females of childbearing potential. Tests will be done at in-person or at home.

\$ Visit windows for Weeks 4-52 are +/-7 days from the baseline visit

% In-person visits

5.2 Study Procedures:

Physical exam: A study physician will conduct a physical examination to ensure the participant is healthy enough to enroll in the study. A pubertal status will also be undertaken by the study physician ([name]) who is a trained pediatric endocrinologist. She has been trained in the proper technique to assess pubertal stages and will be the same study physician conducting all assessments throughout the trial.

Vital signs: Blood pressure (BP) and heart rate (HR) will be collected.

Hemoglobin A1c: Blood will be collected for a hemoglobin A1c level.

EKG: Electrocardiogram will be performed at screening/baseline visit and per PI discretion.

Eating Disorder Examination Questionnaire (EDE-Q): The EDE-Q identifies disordered eating behaviors and unhealthy attitudes about weight, such as purging, unhealthy obsession with dieting and/or body weight, prolonged fasting/starvation, use of laxatives to control weight and excessive exercise.

Patient Health Questionnaire-9 (PHQ-9): The PHQ-9 measures depression and suicidality. The PHQ-9 Modified for Teens will be administered to participants < 18 years of age. A participant will be referred to a mental health professional or primary care provider if s/he has a PHQ-9 score of  $\geq 10$  or reports any suicidal behavior. A PHQ-9 score  $\geq 15$  at the screening vision is an exclusion criteria.

Columbia-Suicide Severity Rating Scale (C-SSRS): The C-SSRS measures depression and suicidality. A participant will be referred to a mental health professional or primary care provider if s/he has any suicidal behavior or any suicidal ideation of type 4 or 5 on the C-SSRS. Please see Exclusion Criteria for cut-off scores related to the C-SSRS.

Pediatric Quality of Life Inventory (PedsQL™): The PedsQL measures general and disease-specific quality of life. We will be using the participant-reported measures for the PedsQL™ Generic Core Scales and Diabetes Module Version 3.2 for young adults (aged 18-25 years) and Teens (12-18 years).

Oral Glucose Tolerance Test (OGTT): Insulin sensitivity and  $\beta$ -cell function will be measured via a 2-hour, 75 mg oral glucose tolerance test. OGTT has been widely used in the evaluation of  $\beta$ -cell dysfunction and T2D, including in the TODAY and RISE studies. The OGTT will be performed following a 10-12 hour overnight fast. Participants will take their last dose of metformin (if applicable) the evening before testing. Participants on basal or bolus insulin will be asked to withhold insulin dose either 36 hours or 6 hours, respectively, prior to testing. Plasma glucose levels, C-peptide, and insulin levels will be measured at baseline, 30, 60, 90 and 120 minutes following standard glucose ingestion. If a participant comes to a visit and has not withheld insulin for the required number of hours, the visit

will proceed without the OGTT and the participant will be asked to return to perform the OGTT within one week of the originally scheduled visit.

Glycemic Control: Time in range (BG of 70-180 mg/dL) and hypoglycemic events will be measured using Continuous Glucose Monitors, either Freestyle Libre 14 day or Dexcom G7. The Freestyle Libre 14 day is no longer being produced so we will phase in the use of Dexcom G7 CGM. Worn on the skin, the disposable, single use sensor will continually measure glucose levels from the interstitium, every minute for 14 days (Libre) or 10 days (Dexcom G7) and will upload the data for review, and the participant will be asked to share this data with the study team. Participants will be taught how to place and replace the CGM. Participants who have a Libre CGM will be instructed to swipe the sensor at least twice daily (fasting and at bedtime) and to upload their CGM data monthly. Participants who have the Dexcom CGM will not need to swipe, but will be instructed to upload their CGM data monthly. CGM data will also be used to titrate insulin and metformin dosing. Percent time of CGM use will be used to assess adherence.

Total daily insulin dose: For participants on insulin therapy, total daily insulin dose (units/kg/day) will be averaged over the previous month at each study visits. Participants will log their insulin doses and return pens to study visits.

Body composition: Total body and visceral fat (% and kg) and measures of bone mineral density will be measured by dual energy x-ray absorptiometry (iDXA). iDXA measurements, using standard positioning techniques, will be conducted and analyzed by trained staff.

Anthropometrics: Height and weight will be collected by trained research staff at weeks 0, 12, 24, 36 and 52. Weight only will be collected at Weeks 4, 8, 16, 20, 28, 32, 40, 44, and 48. Weight will be collected via a scale provided to the participants and reported directly to the research coordinator at Week 28, 32, 40, 44, and 48 if there no monthly visits and per the PI's discretion.

Lifestyle and behavior management: All participants, regardless of drug/placebo assignment, will receive the same lifestyle/behavioral modification counseling monthly throughout the entire study: delivered at each in-person and virtual study visit (screening/baseline visit prior to randomization and weeks 12, 24, 36, and 52). The lifestyle/behavioral modification curriculum has been adapted from the NIDDK-sponsored TODAY study lifestyle modification program materials and is based on principles detailed in U.S. Preventive Services Task Force screening recommendation statement and utilized by our group in a previous and ongoing trials. Trained study coordinators will deliver the lifestyle/behavioral modification counseling, which will focus on small, successive changes in dietary physical activity behaviors through the use of evidence-based behavior change strategies such as self-monitoring, goal setting, reinforcement for goal achievement, stimulus control, social support, problem solving, and motivational techniques.

This will include guidance on a hypocaloric diet (500 calorie per day deficit) and increasing physical activity.

5.3 Study Duration:

This pilot study will enroll approximately 30 participants. Participation will last for approximately 52 weeks.

We anticipate that it will take 36 months to enroll and have all 30 participants complete 52 weeks of treatment.

5.4 Use of Radiation:

The iDXA used in this study uses radiation to generate its picture. The average iDXA is equal to a few hours of ionizing radiation exposure in Minnesota. The AURPAC will be asked to review the consent form language and dosimetry calculations to ensure that they are correct.

**6.0 Data and Specimen Banking:** Not applicable

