### 4.0 Study Intervention(s)/Investigational Agent(s)

#### 4.1 Description:

##### *Phentermine/topiramate Therapy*

Participants randomized to PHN/TPM will initiate treatment at 3.75 mg/23 mg orally once daily in the morning for 14 days, which will then be increased to 7.5 mg/46 mg orally once daily in the morning for 14 days, which will then be increased to 11.25 mg/69 mg orally once daily in the morning for 14 days, which will then be increased to 15 mg/92 mg orally once daily in the morning for the remainder of the trial. There will not be a pause in dose titration between weeks 4 and 12 as indicated by the medication labeling as this pause is indicated to clinically assess weight loss response on mid-dose PHN/TPM before up-titrating to high-dose PHN/TPM. However, the goal of this proposed study is to assess BMI reduction on the maximum tolerated dose of PHN/TPM in a clinical research setting. Therefore, an assessment of weight loss on the moderate dose of

PHN/TPM between weeks 4 and 12 is not warranted. Participants unable to tolerate the dosing regimen will be maintained at the maximally tolerated dose. Following the final study visit, all participants will be down-titrated gradually by taking medication every other day for seven days before stopping treatment altogether. PHN/TPM will be purchased from an independent vendor by the University of Minnesota Investigational Drug Service Pharmacy (IDS). Placebo will be manufactured by IDS. The placebo capsules manufactured by IDS will not be able to be matched to the commercial product. The PI and research coordinator will not be involved in pill counting to evaluate adherence for this trial in order to preserve the blinding of investigators. Participants will not be told which treatment arm they are in to preserve the blinding of participants. Participants will be instructed to take the medication under the supervision of a parent/guardian and pill counts of returned product will serve as a proxy of treatment adherence. If the average fasting plasma glucose (FPG), measured by CGM, is >185 mg/dL after titration to PHN/TPM 15mg/92mg or maximum tolerated dose, metformin therapy or basal insulin therapy will be started or titrated for a goal average FPG <110 mg/dL.

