When an individual participant transitions from the placebo-controlled portion of the study to the open-label portion of the study, the study physician will put in orders for the open label study for IDS to dispense medication and the IDS staff will review the patient randomization and will either continue to fill the prescription with the maintenance dose or fill the prescription to have the participant titrate up on the study medication in order to help keep the study team blinded.

4.3 Biosafety:  
Not applicable.

4.4 Stem Cells:  
Not applicable.

4.5 Fetal Tissue:  
Not applicable

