Weeks 4, 8, 16, 20, 28, 32, 40, 44 and 48: At these timepoints the study staff will review the CGM data, and the participant may be contacted via telephone about adjusting their insulin or metformin dose. Participant will also present to the DCRU to collect study medication as well as upload CGM data if they are unable to do so from home and they will be given new CGM sensors. Monthly urine

pregnancy test results and contraceptive counseling if applicable will also be done when the patient collects their study medication. If participants are able to upload CGM at home, then after week 24, a 2-month supply of study drug and CGM sensors and 2 urine pregnancy tests will be given to participants at visit 24 and a 3-month supply of study medication and CGM sensors and 3 pregnancy tests will be given at visit 36. Study coordinator will then only do a telephone visit for weeks 28, 32, 40, 44, and 48 to review adverse events, home weight, and results of urine pregnancy test.

Week 12 and Week 36: Visits at these timepoints will be conducted at the CRU. Vital signs and weight will be collected. Participants will be asked about any adverse events they have experienced. Contraceptive and lifestyle management counseling will again be given and a pregnancy test will be performed. Participants will have a physical examination and pubertal assessment. Approximately one teaspoon of blood will be drawn for a hemoglobin A1c. Patients will also complete the EDE-Q, PHQ-9, and C-SSRS. Participants will be provided with new CGM sensors and study Medication bottles will be collected and pills counted by the study team to assess compliance. At the Week 12 visit, the pill count will be conducted by a team member not involved in the study so that the study blind is not broken.

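### No blood pressure or heart rate reading is scheduled between baseline and week 12, although the dose rises on days 14, 28 and 42; readings at weeks 4 and 8 would be a cheap safeguard

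*Combined protocol and SAP*

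**What the plan says.** **Readings.** The Schedule of Events row "Vital signs (Blood pressure and heart rate" is marked at screening, baseline and weeks 12, 24, 36 and 52. Section 8.3 matches it. For weeks 12 and 36 it states: "Visits at these timepoints will be conducted at the CRU. Vital signs and weight will be collected". Its entry covering weeks 4 and 8 lists glucose-monitor review, medication, sensors, pregnancy testing and contraceptive counselling, but neither blood pressure nor heart rate. The physical examination row is also blank at weeks 4 and 8.

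**Dose.** Section 4.1 sets three 14-day steps (3.75/23, 7.5/46 and 11.25/69 mg). Of the final increase it says: "which will then be increased to 15 mg/92 mg orally once daily in the morning for the remainder of the trial". It drops the labelled pause between weeks 4 and 12, "as this pause is indicated to clinically assess weight loss response on mid-dose PHN/TPM". It also provides: "Participants unable to tolerate the dosing regimen will be maintained at the maximally tolerated dose".

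**Attendance.** For weeks 4 and 8, section 8.3 says: "Participant will also present to the DCRU to collect study medication". Weight is taken at these visits. Home weights and telephone-only contact begin after week 24: "Study coordinator will then only do a telephone visit for weeks 28, 32, 40, 44, and 48".

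**Open-label phase.** Under section 4.2 the pharmacy checks the original assignment and leaves some participants at maintenance; for the others it will "fill the prescription to have the participant titrate up on the study medication in order to help keep the study team blinded". The titration steps for that phase are not given.

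**The concern.** The plan treats cardiovascular status as relevant at entry. Section 8.2 excludes raised blood pressure, a heart rate of 120 bpm or more, structural heart defects, significant arrhythmia, stimulant use and hypersensitivity to sympathomimetic amines. Section 2.1 describes phentermine as inhibiting norepinephrine reuptake. Yet the whole escalation to the top dose passes without a scheduled on-treatment reading, so the judgement of which dose is tolerated has no scheduled blood pressure or heart rate value behind it.

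At stake is late detection of a rise that causes no symptoms. Monthly adverse-event questioning depends on what participants report. After baseline, an EKG is at the principal investigator's discretion. The data and safety monitoring board receives adverse-event information at least every six months, and an unmeasured rise cannot appear in it.

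**Working it through.** No figure in the plan is in dispute; the check is one of timing. Baseline is day 0.

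**Inputs.** Three 14-day steps (section 4.1); readings at weeks 0, 12 and 24 in the blinded period (Schedule of Events); a window of ±7 days for weeks 4 to 52 (Schedule footnote).

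**Current plan**
- Increases: 14; 14 + 14 = 28; 28 + 14 = 42. The top dose starts on day 42.
- First on-treatment reading: 12 × 7 = day 84, window 77 to 91.
- Time on the top dose by then: 84 − 42 = 42 days; 77 − 42 = 35 and 91 − 42 = 49 at the window edges.
- Increases preceded by an on-treatment reading: 0 of 3.
- On-treatment readings in the blinded period: weeks 12 and 24, so 2.

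**With readings at weeks 4 and 8**
- Week 4 = day 28, window 21 to 35. This is always after day 14, precedes day 28 only if the visit falls on days 21 to 27, and always precedes day 42. One of the three increases is guaranteed a prior reading; two have one if the visit is early.
- Week 8 = day 56, window 49 to 63. This is 56 − 42 = 14 days after the top dose starts (7 to 21).
- First top-dose reading comes earlier by 84 − 56 = 28 days; at opposite window edges, 77 − 63 = 14 and 91 − 49 = 42.
- First on-treatment reading of any kind comes earlier by 84 − 28 = 56 days (nominal).
- On-treatment readings in the blinded period: 2 + 2 = 4.

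**Open-label phase, only if former placebo participants follow the same steps (assumption)**
- Start on day 24 × 7 = 168; increases on days 182, 196 and 210; next reading at week 36 = day 252.
- Time on the top dose by then: 252 − 210 = 42 days. With windows on both visits, 245 − 217 = 28 to 259 − 203 = 56.

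**Reach.** The 15 participants assigned to active drug from week 0, fewer at the top dose if some are held lower. Up to 15 may switch from placebo; 15 × 0.9 = 13.5 at the 10% attrition in section 14.2. The share who will be remote at weeks 28 and 32 is not stated, so readings there could reach none or all of them.

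**What the documents say about the risk.** Table 1 lists tachycardia in 1.8% of 55 clinic patients, which is one patient; it did not resolve and treatment stopped, with dose and timing not given. Table 2 lists no tachycardia among 13 adolescents on 15/92 mg for 56 days. Section 2.2 reports improved blood pressure in adult trials. None of this gives a rate for weeks 0 to 12.

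**The case against.** The best defence is that quarterly readings are deliberate. Section 17.2 says that participants are assessed every three months, and the revision history shows that vital signs at weeks 12 and 36 were added in version 4.0, so the schedule was revisited. Blood pressure and heart rate are named exploratory outcomes, section 14.3 promises continuing review of safety outcomes, participants are told to report any adverse event at once, and the entry limits lower the starting risk. The harm is also unquantified. All of that is fair, and it keeps this a modest point. It does not explain why the whole escalation has no reading, and none of these routes detects a rise without symptoms.

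A reader might infer several stronger things that the documents do not support:
- *That dropping the labelled pause removed a safety check.* Section 4.1 gives the pause a different purpose, judging weight-loss response.
- *That the protocol's data show a cardiovascular hazard.* They neither show nor exclude one.
- *That week-4 and week-8 readings would cover every increase.* Only the day-42 step is guaranteed one.
- *That the section 8.2 limits are a ready-made action rule.* They are entry exclusions (for age 13 and over, 130/80 or more; heart rate 120 or more; each on three measurements). A rise from 75 to 110 bpm, for example, would not trigger them.
- *That the same gap certainly recurs after week 24.* The open-label steps are not stated and attendance in person is optional.

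**Conclusion.** The gap is real, and the Schedule and the visit text agree on it. For participants who titrate on schedule, all three increases come before any scheduled on-treatment blood pressure or heart rate reading, and the first such reading comes about 42 days (35 to 49) into the top dose. Readings at week 12 or 24 can still inform a later hold or step-down, so the issue is delay rather than a complete absence of monitoring.

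This is worth correcting as a cheap improvement to participant safety. The number of participants who would have a raised reading in the gap cannot be estimated from the documents, and the planned efficacy and exploratory comparisons do not change. The conclusion assumes titration at the stated 14-day intervals and attendance at weeks 4 and 8 as section 8.3 describes. The Schedule does not flag those two weeks as in-person, but section 8.3 has participants come in for medication and home weights start only at week 28.

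**What to change.** Add blood pressure and heart rate to the Schedule and to section 8.3 at weeks 4 and 8, in both arms, at the medication pick-up.
- Repeat any raised reading before acting on it.
- Have study clinicians review values against the participant's own baseline as well as the absolute level, instead of adopting the section 8.2 entry limits as the trigger. Dose decisions stay with them.
- Tabulate the values by arm and visit with the safety data.
- Optionally, take the same readings at weeks 28 and 32 from everyone who attends in person, whatever the original arm, so that the act of measuring does not reveal who is titrating.

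The cost is a minor amendment, a few data fields and a few minutes of existing staff time per visit. Some false alarms will need repeat readings and could delay a dose step. The day-14 increase stays uncovered, the day-28 increase is covered only when the week-4 visit is early, and participants who are remote at weeks 28 and 32 are not reached.

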#### 3.3 Exploratory Endpoints/Events/Outcomes

- To evaluate the effects of PHN/TPM on total and visceral body fat
- To evaluate the effects of PHN/TPM vs. placebo + standard treatment on cardiometabolic measures (lipid panel [TC, LDL-C, TG, HDL-C], blood pressure and heart rate).

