### 8.3 Visit Detail:

Screening Visit: After explaining the study in detail, written parental consent and assent will be obtained. If the participant is  $\geq 18$  years of age, the participant consent will be obtained. Potential participants will then undergo screening for inclusion and exclusion criteria (physical exam with height and weight for BMI calculation, Tanner staging for pubertal status. Screening lab [AST, ALT, INR, TSH, bilirubin, albumin, basic metabolic panel will be drawn at this visit and reviewed before setting up the baseline visit. INR, bilirubin, and albumin will be used to determine a Child-Pugh score for hepatic impairment for eligibility. Urine pregnancy test for participants of child-bearing potential will be obtained. BP and HR will be taken. Contraceptive counseling will be provided. The PHQ-9 and C-SSRS will then be completed. All other co-administered medications will be assessed. Participants will then have their medical and medication history collected and demographics collected.

Baseline Visit: Participants who meet eligibility criteria will return for a baseline visit within 4 weeks of the screening visit. Participants will have a physical examination, their height and weight will be measured and their blood pressure and heart rate will be taken. An EKG will be done, and contraceptive counseling will be given. Participants will complete the EDE-Q, and PedsQL. Their daily insulin and metformin doses will be reviewed if applicable. Participants will be instructed how to place and replace a CGM as well as swipe and upload data. The participant will have the OGTT testing and the plasma glucose levels, c-peptide levels and insulin levels taken at outlined timepoints as well as baseline lipid profile, and vitamin D level be drawn at time 0. Approximately 2 tablespoons of blood will be drawn at the visit. The participant will also have an iDXA for total body fat, visceral fat and bone mineral density calculations. Lifestyle management counseling will be given. The participant will then be randomized to receive either PHN/TPM or placebo and will be instructed on how to take the study medication. The participant will be provided with a Bluetooth scale for use at home and to transmit weights to the study team, with a water bottle to encourage water intake and with a drawstring bag to carry the study items.

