Week 24 and Week 52: Participants will present for an in-person visit for a physical examination. Tanner staging, height and weight measurements will be collected. Vital signs (BP and HR) will also be collected. Contraceptive counseling and lifestyle management will again be given. Participants will be asked about adverse events that they have experienced. Blood will be drawn for a hemoglobin A1c, basic metabolic panel, lipid profile, and a Vitamin D 25. A review of the participants' daily insulin doses will be reviewed. Any co-administered medications will be discussed. Participants will have the OGTT testing and blood will be collected at the outlined timepoints for plasma glucose levels, c-peptide levels and insulin levels. Approximately two tablespoons of blood will be drawn at the visit. Participants will be asked to complete the EDE-Q, PedsQL, PHQ-9 and C-SSRS evaluations. Urine pregnancy test will be done and reviewed if applicable. An iDXA for total body fat, visceral fat and bone mineral density will be conducted. The participant will have their CGM data reviewed and new CGM sensors will be provided at week 24. The participant's insulin dose will be reviewed and their adherence to the study medication will be assessed. Study medication will be distributed for week 24. Instructions on how to down-titrate off the study medication will be done on week 52. Participants who elect to upload their CGM data remotely before the visit may elect to receive study medication, home urine pregnancy tests, and sensors to last them for the remainder of the study.

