Exploratory Aim: In an exploratory fashion, we will compare the mean change in total body- and visceral fat (expressed as percent and absolute) and cardiometabolic measures from randomization to 6 months of follow-up between the groups, adjusted for randomization values for added precision.

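### The Schedule of Events marks the lipid profile at baseline only, contradicting section 8.3 and the planned 6-month lipid comparison

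*Combined protocol and SAP*

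**What the plan says.** Section 5.1 introduces its table with the sentence "The schedule of events (below) shows the data that will be collected at each study visit". In that table the row "Lipid profile, vitamin D 1,25" carries a single mark, in the baseline column. The row also carries footnote b, which reads "Blood will be drawn during the OGTT at baseline, 30-, 60-, 90- and 120-minutes following glucose ingestion".

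Section 8.3 describes the same assessments visit by visit. At baseline it agrees with the schedule and gives a draw time: "as well as baseline lipid profile, and vitamin D level be drawn at time 0". For weeks 24 and 52 it states: "Blood will be drawn for a hemoglobin A1c, basic metabolic panel, lipid profile, and a Vitamin D 25".

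Section 3.3 lists, as exploratory, the effect of treatment on "cardiometabolic measures (lipid panel [TC, LDL-C, TG, HDL-C], blood pressure and heart rate". The Exploratory Aim in section 14.3 sets the analysis as a comparison of mean change in "cardiometabolic measures from randomization to 6 months of follow-up between the groups, adjusted for randomization values for added precision".

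**The concern.** The schedule and section 8.3 are both current text, and they give different instructions for the same visits. The opening sentence of section 5.1 presents the schedule as the list of what is collected at each visit, so it is foreseeable that staff would rely on it.

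What is at stake is follow-up data for total cholesterol, LDL-C, triglycerides and HDL-C. A change from randomization to 6 months needs a week-24 value. Section 6.0 says specimen banking does not apply, so the protocol provides no stored sample from which a missed panel could be measured later.

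Two smaller discrepancies sit in the same row. The schedule and the week 24/52 text name the vitamin D assay differently (1,25 against 25), and the baseline text names no assay. Footnote b attaches the five OGTT sampling times to the row, whereas section 8.3 takes the baseline lipid and vitamin D sample once, at time 0.

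**Working it through.** The plan gives no figure to reproduce here. The check is whether the row was read correctly, followed by a count.

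**1. Is the gap real, or a table broken in extraction?** The header has 16 cells: one label and 15 visits (screening, baseline, and 13 visits from week 4 to week 52). The lipid row also has 16 cells, so none was lost. Other rows read the same way serve as controls for alignment:

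| Schedule row | Weeks marked |
|---|---|
| Lipid profile and vitamin D | 0 |
| Liver, thyroid and metabolic labs | -4, 24, 52 |
| Plasma glucose | 0, 24, 52 |
| Vital signs | -4, 0, 12, 24, 36, 52 |

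The controls fall on sensible visits. C-peptide, insulin and iDXA are also marked at weeks 24 and 52. The lipid row has one mark and 13 empty post-baseline cells.

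**2. Does the footnote supply the missing visits?** No. Footnote b sets sampling times within an OGTT. It adds no visit to the row.

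**3. Post-baseline lipid draws per participant under each text.**
- Schedule alone: 0.
- Section 8.3: 2 (weeks 24 and 52).

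**4. What the analysis needs.** For each lipid, change = (week-24 value) - (value at randomization), compared between groups with adjustment for the randomization value. Under the schedule alone the first term does not exist, so the change cannot be formed. Under section 8.3 it can.

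**5. Size.**
- The planned enrolment is 30 (sections 5.1 and 5.3), with one week-24 draw each, so the ceiling is 30 x 1 = 30 draws.
- Each missed panel removes 1/30 = 3.3% of the sample from the comparison.
- Section 3.3 lists six cardiometabolic measures: four lipids, blood pressure and heart rate. The last two are marked at week 24, so the exposure is four of six.
- Section 14.2 bases the primary outcome on BMI. The Aim 2 outcomes in section 14.3 are the C-peptide index, insulin sensitivity, oral disposition index, A1c and daily insulin dose. None uses lipids.

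**6. Partial loss.** Section 14.4 carries the last observation forward for the primary analysis and treats secondary endpoints similarly. It does not mention exploratory ones. If that rule were extended to lipids, a participant with only a baseline value would be assigned a change of zero, pulling that arm's mean change toward zero.

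**The case against.** The strongest reply is that the protocol's intent is not in doubt. The endpoint list, the analysis and the week 24/52 visit text all agree, and one table row is the outlier. The trial's sections on multi-site research say it does not apply, so there are no separate sites to read the table differently. The measures are exploratory. All of this stands, and it keeps the point modest. It does not remove the point, because the protocol itself presents the table as the statement of what is collected.

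Three stronger readings are tempting, and the documents do not support them.

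- A reader might infer that the trial has no plan to collect 6-month lipids and that the comparison cannot be done. Section 8.3 orders the draw, so this is a contradiction between two places, not an assessment missing from the protocol.
- A reader might count 30 x 2 = 60 lost draws. The planned between-group comparison stops at 6 months, so the 30 week-52 draws do not feed it. Even 30 is a ceiling: it assumes that section 8.3 is ignored for every participant.
- A reader might argue that triglycerides are the reason for choosing this drug. Section 2.1 does express interest in a triglyceride result, from adolescents without diabetes. Its stated rationale for the choice is availability of the drug, oral dosing and several mechanisms acting on weight.

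The vitamin D discrepancy is a fair correction but adds nothing to the analytic harm, since vitamin D is not a listed outcome.

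One further objection bears on the remedy. Simply deleting footnote b would leave the week-24 and week-52 samples with no stated timing relative to the glucose load, because section 8.3 gives time 0 for baseline only. That objection is right, and the fix allows for it.

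**Conclusion.** The point holds as an internal contradiction. The schedule omits week-24 and week-52 lipid draws that section 8.3 orders, and the exploratory analysis depends on the week-24 one. If staff worked from the schedule alone, up to 30 draws feeding the planned comparison would be missed, and four exploratory lipid measures would lack a follow-up value. Blood pressure, heart rate, the primary outcome and the Aim 2 outcomes are unaffected.

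The size rests on two assumptions: that all 30 participants reach week 24, and that the schedule is followed in preference to section 8.3. The documents do not show how likely the second is, so the loss could lie anywhere from 0 to 30 draws. The entry on lipid timing in the revision history was not relied on, because an amendment log is not current text.

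**What to change.** - In the Schedule of Events, mark the lipid and vitamin D row at weeks 24 and 52, so that it agrees with sections 8.3 and 14.3.
- Replace footnote b on this row with a note that the sample is drawn once, at OGTT time 0. Section 8.3 already says this for baseline; state the same timing there for weeks 24 and 52. Because section 5.2 allows the OGTT to move to a return visit, the note should also say whether this sample moves with it.
- Reconcile the vitamin D assay name across the schedule and section 8.3. The documents do not settle which is meant, so the sponsor must.
- Check whether week-24 lipids were obtained for participants already seen, and report the number missing by arm if any were not.

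The cost is a correction to one table row and matching text. The schedule already has blood drawn at weeks 24 and 52 for A1c, the metabolic panel and the OGTT samples, so no visit or procedure is added.
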